### 6.3 Stratification Factors

N/A: this is not a randomized study.

### 6.4 Stratification factors and their impact on design

The analysis will be stratified on the time of follow-up, volumetric and BIS changes, as well as self-reported symptoms will be correlated at the corresponding time points.

### 6.5 Early stopping rules, if appropriate

N/A: the study will not have early stopping rules.

### 6.6 Definition of and allowance in design for unevaluable / ineligible participants

Only eligible patients, as specified by inclusion and exclusion criteria, will participate in this study. In the event that a participant is found to be ineligible according to the exclusion criteria after enrollment into the study, the patient will be removed and the QACT will be notified. All data corresponding to these patients will be excluded in the analyses. If a participant becomes ineligible according to the exclusion criteria while actively enrolled in this study, the participant will be removed and the QACT will be notified. Any data corresponding to these patients collected prior to removal will be included in the analyses. The sample size for this study takes into account potential unevaluable/ ineligible participants by aiming to accrue 200 participants, when only 160 non-missing pairs of measurements overall are needed to meet the desired confidence interval for statistical analysis.

### 6.7 Analysis plan

The statistical analysis in this study will subsist in 1) calculating the Kendall's correlation coefficient with 95% confidence intervals for each time point, separately for all subjects and in the subgroup with  $RVC \geq 5\%$ , 2) plotting graphically the relationship between changes in arm volumes and BIS measurements, by time point, 3) calculate overall Kendall's tau stratifying by time point, i.e., evaluating concordant and discordant pairs within each time point only (35), 4) determining the change of BIS measurements

corresponding to RVC=5% of volumetric measurements, 5) calculating area under ROC curve, for predicting volumetric RVC $\geq$ 5% using BIS measurements, and tabulating diagnostic indices including specificity, sensitivity, positive prognostic value, 6) evaluating diagnostic characteristics of lymphedema diagnosis based on BIS using 3 sigma method, and 7) assessing the association between patient-reported symptoms and each measurement method (using area under ROC and other diagnostic criteria). We will also evaluate the statistical distribution of BIS measurements and based on the shape of the distribution determined if BIS changes are better captured as absolute or as relative differences.

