## 2.0 OBJECTIVES

### 2.1 Primary Objectives:

- To assess the validity of BIS as a tool for quantification of lymphedema through comparison with perometry
- To determine relationship between impedance ratios, relative volume changes (RVC), and self-reported symptoms

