### *Perometer*

The perometer is a well-validated instrument for quantifying volume in a limb, and has been a regular part of the standard of care for MGH breast cancer patients since 2005. Patients are routinely measured (1) at diagnosis, (2) after surgery, (3) after chemotherapy, (4) after radiation, (5) at four to seven month follow-up visits that continue for five years, and (6) any time a patient reports with new symptoms of swelling or arm discomfort outside these time frames. The perometer provides highly reliable and valid arm volume measurements, with no physical discomfort or inconvenience to the patient. It utilizes infrared lamp-light receiver pairs contained within a frame which is moved along the extremity. As indicated by our preliminary analyses and the literature, the perometer calculates volume within 1% accuracy (33). This calculation of volume is accurate within a standard deviation of 8.9 ml and a .55% difference with repeated measurements (33). The perometer can give detailed information about arm volume in milliliters, the percent difference between the volumes of both arms, the location of the swelling in the arm as well as a follow-up clearly showing progression of the lymphedema over time.

Measurements of arm volume with the perometer will be taken pre- and post-operatively, as well as at screening visits per study design. All arm volume measurements will be converted to a percent RVC. The RVC calculation will indicate volume changes in the affected arm as compared to the baseline measurement. This value will indicate whether or not a patient is experiencing lymphedema for the purposes of this study and will determine patient eligibility for enrollment into Partners Protocol 08-308.

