### 6.2 Sample Size and Statistical Power

The sample size will be determined with the prospect of primary aim of this study, i.e, to evaluate the correlation between arm volume changes measured by perometry and quantified using RVC formula (26) and using relative changes of impedance measured by biimpedance spectroscopy (BIS). We want to evaluate this correlation for all subjects enrolled, and separately, for a subgroup of those subjects who develop lymphedema with  $RVC \geq 5\%$ . The first analysis will evaluate overall agreement between these two techniques and the second analysis will evaluate agreement between assessment of lymphedema grade by both techniques. We plan to quantify the relationship between these two measurement methods using Kendall's tau coefficient (34).

We chose to use a non-parametric correlation coefficient to account for a possible non-linear form of the relationship between the two measurements, and for a possible non-normal distribution of BIS measurements. We expect a moderately high correlation between these measurements,  $\tau = 0.50$ . The choice of sample size is motivated by a need to evaluate the correlation with sufficient precision rather than by a hypothesis test: we want to obtain a lower bound of 95% confidence interval for the estimate of tau of no less than 0.2 in the LE group and of no less than 0.42 overall. We assume that 10% of enrolled subjects will develop lymphedema with  $RVC \geq 5\%$ . Furthermore, we expect that up to 20% of paired measurements may be missing due to non-compliance or technical problems.

Sample size calculations are based on approximate confidence intervals for Kendall's tau (35). The minimum number of measurements, to attain the required precision in the LE group is n=16; however, accounting for missing data we need to enroll 20 patients with LE and 200 patients overall. We thus expect to have 160 non-missing pairs of measurements overall, this allows us to determine Kendall's tau with 95% confidence interval from 0.426 to 0.567.

Of note, patients that are enrolled pre-operatively and subsequently undergo bilateral breast surgery, rendering them ineligible for the study, will not be counted towards the overall accrual goal of 200 subjects.

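### The first primary objective is quantification, but Kendall's tau measures ranking and nothing in 6.7 estimates the spread of RVC around a given BIS change

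*Combined protocol and SAP*

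**What the plan says.** Section 2.1 gives the first primary objective as "To assess the validity of BIS as a tool for quantification of lymphedema through comparison with perometry" and the second as "To determine relationship between impedance ratios, relative volume changes (RVC), and self-reported symptoms". Section 6.2 names Kendall's tau as the statistic linking the two methods. It says of the analysis in all subjects: "The first analysis will evaluate overall agreement between these two techniques". A second analysis, in women with RVC of 5% or more, is likewise described as agreement on lymphedema grade. The expected tau is 0.50 ("We expect a moderately high correlation between these measurements"). The sample size is set by precision: the lower 95% confidence limit for tau is to be "no less than 0.2 in the LE group and of no less than 0.42 overall".

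Section 6.7 then lists seven items:

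- Items 1 and 3: tau by time point, and overall stratified by time point.
- Item 2: "plotting graphically the relationship between changes in arm volumes and BIS measurements, by time point".
- Item 4: the BIS change that corresponds to RVC=5%.
- Item 5: ROC area for RVC of 5% or more, with sensitivity, specificity and positive predictive value.
- Item 6: diagnostic performance of the 3 sigma BIS rule.
- Item 7: association of symptoms with each method.

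A closing sentence chooses between absolute and relative BIS change. Section 6.1 plans an RVC-like formula for BIS. Section 1.2.1 states that impedance and limb volume cannot be compared directly because no mathematical relation links their units.

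**The concern.** An objective about quantification asks how much swelling a BIS reading stands for, and how closely. Tau asks whether women with a larger BIS change also tend to have a larger RVC. A good answer to the second question is not an answer to the first, yet 6.2 calls the result agreement.

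No item in 6.7 supplies the missing quantity. Item 4 gives one conversion point with no stated method and no spread. Items 5 and 6 count misclassification on either side of a cut-off, which is useful but is not a size of error. Item 2 would show the scatter without putting a number on it.

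At stake is the reporting of the first primary objective. A tau near the expected 0.50, with a tight confidence interval, could be presented as validating BIS for quantification while the report contains no figure for how widely RVC varies among women with the same BIS change.

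**Working it through.** **1. The plan's own figure.** Inputs from 6.2: tau=0.50, 160 non-missing pairs overall, 16 in the lymphedema group, 95% confidence. Under bivariate normality r = sin(π·tau/2) = sin(π/4) = 0.7071. Take a Fisher z interval on r with standard error 1/√(n−3), and map back by tau = (2/π)·arcsin(r).

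- n=160: atanh(0.7071) = 0.881; 1.96/√157 = 0.156; the tau limits are 0.426 and 0.567, exactly as stated.
- n=16 gives a lower limit of 0.211 and n=15 gives 0.198, so 16 is the minimum for 0.2, as stated.
- 16/0.8 = 20, 160/0.8 = 200 and 20/0.10 = 200, as stated.

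The sample-size arithmetic is therefore sound. It gives precision for a rank statistic.

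**2. What tau can and cannot see.** Tau is unchanged by any increasing transformation of either variable. In 160 simulated pairs, tau was 0.5215 with BIS on the RVC scale. It was still 0.5215 after BIS was multiplied by 2.5 and shifted by 10, and again after an exponential transformation. Between the first two versions the mean difference from RVC moved from −0.2 to 10.2 and the SD of the differences from 3.5 to 9.2. ROC area is also rank-based.

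**3. Spread implied by the expected tau.** This uses the same normal link as step 1. The residual SD of RVC given BIS is SD(RVC)·√(1−r²), and the 95% half-width is 1.96 times that.

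| tau | r | r² | half-width, in SDs of RVC |
|---|---|---|---|
| 0.42 (target lower limit) | 0.613 | 0.376 | 1.55 |
| 0.50 (expected) | 0.707 | 0.500 | 1.39 |
| 0.567 (upper end of the stated interval) | 0.777 | 0.604 | 1.23 |

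**4. In RVC points.** The documents do not give the SD of RVC. As an assumption, back-solve it from a normal distribution: SD = (5 − mean)/z(1 − share of readings at 5% or more), with z = 1.282 for a 10% share and 1.645 for a 5% share.

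| share of readings ≥5% | mean RVC | SD | half-width, tau=0.50 | range around predicted 5% |
|---|---|---|---|---|
| 10% | 0 | 3.90 | 5.41 | −0.4 to 10.4 |
| 10% | 1 | 3.12 | 4.33 | 0.7 to 9.3 |
| 5% | 0 | 3.04 | 4.21 | 0.8 to 9.2 |
| 5% | 1 | 2.43 | 3.37 | 1.6 to 8.4 |

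At tau=0.42 the half-widths run from 3.77 to 6.04. The width is proportional to the SD, so at tau=0.50 each further point of SD adds 1.39 points.

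**5. Can the planned data estimate it?** From the chi-square distribution on n−2 degrees of freedom, 160 independent pairs fix the residual SD to within about −10% to +12%. Sixteen pairs fix it only to within −27% to +58%.

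**The case against.** **The protocol frames its aim mainly as detection.** Sections 1.1, 1.2.4 and 5.5 speak of early detection, monitoring, and relating the BIS scale to established definitions, which items 4 to 6 serve. This has weight, and the diagnostic and symptom aims are covered. But 2.1 says quantification and 6.2 says agreement, and those words are not served by ranks and cut-offs.

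**The units differ.** That rules out subtracting one measurement from the other. It does not rule out calibrating RVC on BIS change. Tau was chosen in 6.2 to allow for non-linearity and non-normality, and a monotone or quantile fit respects both.

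**BIS targets extracellular fluid,** so scatter of RVC around BIS is not purely BIS error. This is correct. The interval describes how well BIS stands in for RVC, not a fault in the device.

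**Tempting stronger readings.** A reader might infer from the widest range that a BIS value cannot tell no swelling from established swelling. The documents do not support that. Only one of the four scenarios at tau=0.50 reaches 0% or the 10% that opens the moderate band in 1.2.2. That scenario puts 10% of readings at or above 5%, whereas the plan's 10% is of enrolled subjects. Items 5 and 6 would also report misclassification at the cut-offs. A reader might likewise set the half-width against the perometer figure in 5.2 ("This calculation of volume is accurate within a standard deviation of 8.9 ml and a .55% difference with repeated measurements"). That is a repeat-volume figure of unspecified type, not a 95% limit for RVC, so the two are not like for like.

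**Conclusion.** The point holds as a gap in the analysis of the first primary objective. Tau is described as agreement but measures ranking, and the numerical spread of RVC at a given BIS change is not estimated anywhere in the plan. The plan's confidence interval and sample size are correct for tau.

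On size, if tau is 0.50, about half of the RVC variance is left unexplained and individual 95% limits are about ±1.39 SD of RVC, or roughly ±3.4 to ±5.4 points around a predicted 5%. The fraction rests on bivariate normality. The points rest also on assumed means and shares of readings, because the documents give no SD of RVC. These figures illustrate why the quantity should be estimated; they do not predict the result.

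It might seem to follow that tau should be dropped or that the conclusion should rest on the interval alone. Neither is needed. Tau remains a legitimate measure of association and the basis of the sample size, and an interval with no agreed acceptable width would not settle validity by itself.

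**What to change.** - Extend 6.7 item 4. Fit RVC on BIS change across paired visits with a monotone spline or quantile regression, resampling by woman because visits repeat. Report the fitted curve with a 95% prediction interval for an individual's RVC over the observed BIS range, and explicitly where predicted RVC is 5%. Treat higher values as descriptive only.
- Reword 6.2 so that tau is described as rank association, both overall and in the subgroup with RVC of 5% or more. Keep it as the sample-size statistic.
- State that the conclusion on quantification is to be read from tau and the prediction interval together.

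The cost is some plan wording and one added analysis of measurements already scheduled under 5.4, with no further patients or visits. The interval will be imprecise at high RVC because few women are expected there, and the result may look less favourable than tau alone.

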#### **7.0 REFERENCES**

#### **8.0 APPENDICES**

## 1.0 INTRODUCTION

### 1.1 Overview

Prior studies of bioimpedance spectroscopy for the detection of lymphedema have left significant gaps in the literature regarding its use as a tool for the early detection of breast cancer-related lymphedema and its relationship with previously established measurement methods and self-reported symptoms. The purpose of our study is to assess for lymphedema pre- and post- treatment (surgery, +/- radiation, +/- chemotherapy) through the concurrent use of perometry, bioimpedance spectroscopy, and self-report. From these assessments we will:

- 1) Determine if BIS is a valid tool for early detection of lymphedema through comparison with the perometer and self-reported symptoms
- 2) Evaluate the relationship between impedance ratios obtained through bioimpedance, volume changes measured by perometry and quantified using the relative volume change equation (RVC), and self-reported symptoms.

From this data we will determine if bioimpedance spectroscopy is a valid tool for detecting and monitoring of early lymphedema. Furthermore we aim to determine the relationship between diagnostic indices utilized by perometry and BIS such that measurements with BIS can be related to the previously established definitions of lymphedema and used in a clinically meaningful way.

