Additionally, in order to evaluate the efficacy of early intervention for mild and moderate edema, our team developed DFHCC Protocol #2008P-000308, in which a sample of women who experience mild and moderate volume changes are randomized to postoperative compression. If during the course of a patient's screening visits as part of Protocol 2008P-000540 they are found to have an RVC of  $\geq 5\%$ , which remains above 5% at a verification measurement within 4-8 weeks, the patient may enroll in the intervention arm of the study. Dependent upon their RVC, these patients are randomized either within Group I –Mild Lymphedema ( $5\% < 10\%$  RVC) or Group II – Moderate Lymphedema ( $\geq 10\% - 20\%$  RVC). Patients with mild lymphedema are randomized either to observation or compression, and those with moderate lymphedema are randomized either to compression or compression with night compression bandaging.

In the proposed study, we aim to prospectively screen a cohort of patients with bioimpedance spectroscopy, in addition to the perometer and LEFT-BC questionnaire to determine if BIS is a valid clinical tool for assessing lymphedema in breast cancer patients. Through the collection of concurrent longitudinal measurements with the perometer and BIS, we will establish the relationship between these assessment methods, as well as evaluate the symptoms, functional disability, and changes in quality of life that accompany these measurements. This study will be and all previous studies were supported by 2 NIH grants totally  $> \$2.2M / 5$  years [Award Number R01CA139118 (PI: [name]), Award Number P50CA089393 (PI: [name])].

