#### 5.4 Data Collection

Patients will be assessed pre-operatively, at the initiation and conclusion of each type of treatment (surgery, chemotherapy and radiation), and every 4-12 months following the completion of treatment for a period of 24 months. Subsequently they will be assessed at the time their follow-up appointments with their oncologists, with no more than 20 months between measurements. At the time of each assessment, the patient will be measured with the perometer, bioimpedance spectroscopy, and will complete the LEFT-BC questionnaire. Data collected at each visit includes arm volume measurements obtained via perometry and quantified using the RVC equation, bioimpedance ratios collected via BIS, self-reported symptoms obtained via the LEFT-BC questionnaire.

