#### 5.5 Description of Study Process

The proposed study will incorporate the use of bioimpedance spectroscopy (BIS) to evaluate its validity for detecting and monitoring lymphedema. Patients will be assessed for lymphedema in a prospective manner using perometry, BIS, and the LEFT-BC questionnaire, accruing a total of 200 patients in 5 years. The entire study will be

completed at the MGH main campus, and all patients who present for a baseline (pre-operative) arm measurement and meet the eligibility criteria will be offered the opportunity to participate in this trial. At this time the purpose of the trial will be explained, and any patient that wishes to participate will be assessed using the perometer, BIS, and provided with the LEFT-BC questionnaire to complete prior to surgery. Patients who do not wish to participate in the proposed trial will be asked to participate instead in Partners Protocol #2008P-000540, which involves regular assessment with the perometer and completion of the LEFT-BC questionnaire at the time of each perometer measurement.

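### The plan claims to judge BIS for monitoring, but no analysis in 6.7 asks whether BIS and arm volume move together within a woman across her follow-up visits

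*Combined protocol and SAP*

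**What the plan says.** Section 1.1 says the data will determine whether BIS is a "valid tool for detecting and monitoring of early lymphedema". Section 5.5 says the study uses BIS "to evaluate its validity for detecting and monitoring lymphedema". Section 1.2.2 says the relationship between the methods will be established through "collection of concurrent longitudinal measurements with the perometer and BIS", and section 5.4 schedules repeated joint visits: before surgery, around each treatment, "every 4-12 months following the completion of treatment for a period of 24 months", and at longer intervals after that.

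Section 6.4 states: "The analysis will be stratified on the time of follow-up". In section 6.7, item 1 is "calculating the Kendall's correlation coefficient with 95% confidence intervals for each time point", item 2 is a set of plots by time point, and item 3 is an overall tau obtained by "evaluating concordant and discordant pairs within each time point only". Items 4 to 7 cover the BIS change that corresponds to RVC=5%, the ROC curve and diagnostic indices, the 3-sigma rule, and the association with symptoms.

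The variables being correlated are changes from the woman's own pre-operative reading. Section 5.2 defines RVC that way, section 6.1 plans a similar formula for BIS, and section 6.8 requires both a baseline and a follow-up reading.

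**The concern.** Monitoring means following one patient over time. When her arm volume goes up or down between visits, her BIS reading should do the same. The planned taus ask a related but different question: at a given visit, do the women whose volume has risen most since baseline also show the largest BIS change? Item 3 excludes by construction every pair of visits from the same woman, and items 4 to 7 contain no comparison across a woman's follow-up visits.

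The two questions can have different answers. Part of each change score stays with the woman at all her visits. Lasting swelling is one source. Another is the error in her single baseline reading, which enters every later change. Agreement on that stable part raises the per-visit tau without showing that the measures track each other from visit to visit. A good per-visit tau could then be reported as validating monitoring, although the trial holds the repeated readings that would address monitoring directly.

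**Working it through.** **The plan's own figure.** Section 6.2 takes tau = 0.50 and prints a 95% interval of 0.426 to 0.567 for 160 pairs. On the Fisher-z scale, tanh(atanh 0.50 ± 1.96·√(0.36/156)) gives 0.426 to 0.567. The constant 0.36 was back-solved to match and is not in the documents. With 0.437 (the Fieller variance) the interval is 0.418 to 0.574. The enrolment chain also holds: 16/0.8 = 20, 20/0.10 = 200, 200×0.8 = 160. All of this concerns the precision of one cross-sectional tau with one pair per woman. None of it bears on tracking within a woman.

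**What a per-visit tau of 0.50 implies.** Assume normal data, and split each change score into a stable person part (variance share L, the same for both measures) and a visit part. Let rb be the correlation between the two measures' stable parts, and rw that between their visit parts.

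- Per-visit correlation: r = L·rb + (1−L)·rw
- Link to tau under normality: r = sin(π·0.50/2) = 0.707
- Hence rw = (0.707 − L·rb)/(1−L), and within-woman tau = (2/π)·arcsin(rw)

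If a fraction e of the stable part is baseline error not shared by the two devices, and the rest agrees perfectly, then rb = 1−e. The documents give neither L nor e, so both are assumptions.

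| L | e | rb | rw | within-woman tau |
|---|---|---|---|---|
| 0.50 | 0 | 1.00 | (0.707−0.500)/0.50 = 0.414 | 0.27 |
| 0.50 | 0.25 | 0.75 | (0.707−0.375)/0.50 = 0.664 | 0.46 |
| 0.50 | 0.50 | 0.50 | (0.707−0.250)/0.50 = 0.914 | 0.73 |
| 0.75 | 0 | 1.00 | (0.707−0.750)/0.25 = −0.17 | −0.11 |
| 0.75 | 0.25 | 0.75 | (0.707−0.5625)/0.25 = 0.578 | 0.39 |

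At L = 0.50 the within-woman tau approaches 1 when rb falls to about 0.41. A simulation of 160 women with six follow-up visits (an assumed number) agrees: a visit-stratified tau of about 0.50 went with within-woman taus of about 0.00, 0.34, 0.50 and 0.79 under different splits.

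**What the planned tau does pick up.** In the same kind of simulation, when stable levels are strongly related (raw-level tau 0.51) but the women's own changes are unrelated, the planned change-score tau is 0.00. When own movements are coupled at 0.707, it is 0.50. The planned tau therefore does respond to own change from baseline.

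**Data available.** With five follow-up visits per woman (assumed) there are 160×10 = 1,600 same-woman visit pairs. With four visits there are 160×6 = 960, and with ten there are 160×45 = 7,200. Pairs from one woman are not independent.

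**The case against.** A reader might infer that the plan never looks at whether a woman's BIS moves with her own arm volume. The documents do not support that. RVC and BIS change are both measured from her own baseline (5.2, 6.1, 6.8), so the per-visit taus are between-woman evidence about own change. Items 4 and 5 of section 6.7 also use own-baseline quantities. Nor do the repeated readings go unused, since items 1 to 3 draw on every time point. What is absent is narrower: a comparison across follow-up visits within a woman.

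A reader might also infer that a tau of 0.50 says almost nothing about within-woman tracking. That rests on the extreme case in which the stable parts of the two devices agree perfectly. Unshared baseline error makes perfect agreement impossible and raises the lower figure, as the table shows.

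Three further objections have weight. First, monitoring appears in sections 1.1 and 5.5 but is not named in objectives 2.1 and 2.2 or in 6.1, so narrowing the wording is a legitimate alternative remedy. Second, stratifying by time point is defensible, because it removes time trends common to all women. Third, an all-women within-patient tau can mislead. The plan assumes that only 10% of women reach RVC≥5%, and visit differences in the rest may be mostly noise. In an illustrative simulation (90% with no true movement, 10% moving with an SD five times the device noise, five visits), the within-woman tau was 0.82 in the women who moved but 0.08 overall. This does not single out the added analysis, because the planned all-women per-visit tau was also low in that scenario, at 0.14. It is a reason to report the RVC≥5% group separately and to put the weight there.

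**Conclusion.** The gap is real but limited. The plan addresses own change from baseline cross-sectionally at each visit and has no within-woman analysis across follow-up visits. The monitoring claim in 1.1 and 5.5 is therefore only partly supported. A per-visit tau of 0.50 leaves the within-woman value open: under an assumed 50% stable share it could be as low as 0.27 with perfect stable agreement, about 0.46 if a quarter of the stable part is unshared baseline error, or much higher. These figures rest on normality, an equal stable share in both measures, and a variance split that the documents do not give. They show that the quantity is not identified. They do not predict that BIS tracks poorly. The sample size is not affected.

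**What to change.** Add a supplementary item to section 6.7: Kendall's tau between RVC and BIS change, with concordant and discordant pairs formed within patient across her follow-up visits (patient as stratum in place of time point) and a patient-clustered 95% confidence interval. Report it for all women and separately for women who ever reach RVC≥5%. Base any monitoring statement on this analysis, chiefly on the RVC≥5% group, read alongside the per-visit taus. The alternative is to limit the conclusions in 1.1 and 5.5 to detection and cross-sectional agreement of change from baseline.

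The choice that 6.7 leaves open, between absolute and relative BIS change, does not affect this estimate. A woman's baseline is constant, so for a positive baseline both forms rank her visits identically.

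The cost is plan wording and one more analysis run on data already being collected. The downsides should be stated in the plan: one more reported coefficient; an imprecise subgroup estimate, since section 6.2 implies about 16 to 20 women and some may enter the compression trial (5.3); and an all-women figure diluted by measurement noise in women whose arms do not change.

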More recently, bioelectrical impedance analysis (BIA) has also been utilized for the detection of breast cancer-related lymphedema. BIA measures the opposition to flow of an electric current passed through the body at single or multiple frequencies, and resistance to the flow of this current is reported as an impedance value. The level of impedance to a current depends upon the capacitive and inductive properties of the medium through which the current is passed (22). Single-frequency bioimpedance analysis (SF-BIA) devices pass an electrical current through the body at only one frequency (23), whereas multiple frequency bioimpedance analysis (MF-BIA) and bioimpedance spectroscopy (BIS) utilize multiple frequencies and can detect fluid volume changes specifically related to extracellular fluid (22). Increased fluid in the extracellular space of the limb, as occurs in lymphedema, decreases resistance to current flow and results in a lower impedance value (24,25). It has been established that increased limb volume based upon circumferential measurements correlates with a decreased impedance value obtained via BIA (24).

To quantify lymphedema using bioimpedance analysis, the ratio of impedance values of the affected to unaffected limb is calculated. The difference between the measured impedance ratio and an established normal range is then assessed as standard deviations from the norm, and 3+ deviations is considered to be indicative of lymphedema (23). Since there is no direct mathematical relationship between impedance (in ohms) and volume (in ml) of the limb, it is not possible to directly compare impedance values obtained using BIA with limb volume changes obtained from circumferential or volumetric measurements (24).

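### Does Section 6.7 item 4 need a named estimator for the BIS change that corresponds to RVC=5%?

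*Combined protocol and SAP*

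**What the plan says.** Item 4 of Section 6.7 consists of "determining the change of BIS measurements", continuing "corresponding to RVC=5% of volumetric measurements". It gives no model, regression direction, rule for combining visits or interval. Section 6.1 says that BIS change will be quantified by a formula similar to RVC once its distribution has been examined, and Section 6.7 leaves open whether the change is absolute or relative. Section 6.4 stratifies the analysis by follow-up time. None of these defines the correspondence.

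The neighbouring items are separate analyses:

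- Item 1 is "calculating the Kendall's correlation coefficient with 95% confidence intervals for each time point".
- Item 5 is "calculating area under ROC curve, for predicting volumetric RVC" at or above 5%, together with "tabulating diagnostic indices including specificity, sensitivity, positive prognostic value". It names no cut-off for that table.
- Item 6 is "evaluating diagnostic characteristics of lymphedema diagnosis based on BIS using 3 sigma method".

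The background (Section 1.2.1) notes that "there is no direct mathematical relationship between impedance (in ohms) and volume (in ml) of the limb". The overview (Section 1.1) wants the diagnostic indices linked "such that measurements with BIS can be related to the previously established definitions of lymphedema". Sections 2.2 and 6.1 list a BIS threshold for intervention among the secondary aims.

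**The concern.** If impedance does not convert directly to volume, the BIS value matching RVC=5% has to be estimated from the paired data. Kendall's tau cannot supply it, because it measures association and gives no mapping. When correlation is imperfect, BIS predicted from RVC and RVC predicted from BIS are different lines, and they reach RVC=5% at different BIS values. Matching percentiles of the two distributions gives a third value.

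Item 4 starts from RVC, while item 5 treats BIS as the predictor, so the sentence can be read as pointing both ways. If sensitivity were then quoted at the item 4 cut-off, the method could decide whether BIS seems to detect most patients with RVC≥5% or few of them. An unstated method could also be chosen after the results are known.

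**Working it through.** **The plan's own figures.** Section 6.2 assumes tau = 0.50, 10% of subjects developing RVC≥5% and up to 20% of pairs missing. The enrolment arithmetic holds: 16/0.8 = 20 patients with lymphedema, 160/0.8 = 200 overall, and 20/0.10 = 200.

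For the interval I used the variance of tau under bivariate normality:

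var = 2/[n(n−1)] × {1 − 4·asin(r)²/π² + 2(n−2)[1/9 − 4·asin(r/2)²/π²]}, with r = sin(π·tau/2) = 0.7071.

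At n = 160 the standard error is 0.0388. On the Fisher z scale, atanh(0.50) ± 1.96 × 0.0388/0.75 gives 0.420 to 0.572, against the stated 0.426 to 0.567. The smallest n is 160 for a lower bound of 0.42, as planned, and 18 for a lower bound of 0.2, against the stated 16. The small differences depend on the variance formula. No item 4 quantity enters this calculation.

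**Illustration of the gap.** Assumptions: bivariate normality, 10% with RVC≥5% at the visit analysed, and cut-offs in SDs above the mean BIS change. RVC=5% then lies at z = 1.2816 on the RVC scale. Sensitivity, specificity and positive predictive value (PPV) come from integrating the bivariate normal.

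| Method | Cut-off | Sensitivity | Specificity | PPV | Above cut-off, of 200 |
|---|---|---|---|---|---|
| BIS on RVC | r·z = 0.906 | 0.666 | 0.871 | 0.365 | 36 |
| Percentile matching | z = 1.282 | 0.474 | 0.942 | 0.474 | 20 |
| RVC on BIS, inverted | z/r = 1.812 | 0.225 | 0.986 | 0.643 | 7 |

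The ratio of the two regression cut-offs is 1/r² = 2.00. The last sensitivity is 0.2248 before rounding.

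**How far this depends on the assumptions** (sensitivity, BIS on RVC against inverted RVC on BIS):

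| Case | Sensitivities | Ratio of cut-offs |
|---|---|---|
| tau 0.426, 10% | 0.64 vs 0.12 | 2.60 |
| tau 0.567, 10% | 0.70 vs 0.34 | 1.65 |
| tau 0.50, 5% | 0.65 vs 0.13 | 2.00 |
| tau 0.50, 25% | 0.70 vs 0.47 | 2.00 |

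The first two rows use the ends of the plan's stated interval for tau. Three qualifications apply.

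- Section 6.2 chose tau because the relation may be non-linear and BIS non-normal, so normality is not the plan's assumption.
- The 10% is the share who will ever develop RVC≥5%, not the prevalence at one visit.
- The factor of 2 applies to distances from the mean. With an assumed mean BIS change of 0.5 SD, the ratio of raw cut-offs is (0.5 + 1.812)/(0.5 + 0.906) = 1.64. With a mean of 1 SD it is 2.812/1.906 = 1.48.

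**What item 4 feeds.** The ROC area in item 5 uses every cut-off and does not change with item 4. Item 6 uses its own 3-sigma rule. The rows of the first table are three points on one ROC curve, and the gain in specificity from 0.871 to 0.986 accompanies the loss in sensitivity.

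**The case for a change.** The strongest case for a change is that the gap is real and is not sampling noise. In 20,000 simulated samples of 160 under normality, the 95% ranges of the two least-squares cut-offs were 0.73 to 1.09 SD and 1.53 to 2.19 SD. They do not overlap, so more patients would not settle the choice. Nor does it vanish without normality. At tau = 0.50 and 10%, using conditional medians, the sensitivities are 0.68 vs 0.31 under a t copula with 4 df, 0.74 vs 0.45 under a Gumbel copula and 0.80 vs 0.60 under a survival Clayton copula. Under Frank and Clayton copulas no BIS value has a median RVC at the 5% level, so the inverted reading gives no cut-off. A few sentences would close the matter without new data.

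It stands that item 4 names no estimator, and that the candidates differ by more than chance. The rest carries less weight:

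- Reading item 5 as a regression of RVC on BIS is a construction. It is a ROC analysis and fits no such line.
- The precision argument for BIS on RVC (SD 0.09 against 0.17) is an effect of scale. Relative to their means the two are 0.092/0.906 = 10% and 0.169/1.825 = 9%.
- Median regression, inverse regression, percentile matching and a ROC-based rule answer slightly different questions. Fixing one would record a preference.
- The source of sigma is partly covered, since Section 1.2.1 describes 3 deviations from an established normal range. Intervals for the diagnostic indices and allowance for repeated visits are routine details of reporting.

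**Conclusion.** The omission is real and of low consequence, and no change to the plan follows. No stated rule gives a wrong result. Item 4 sets RVC at 5% and asks for BIS, so the natural analysis is BIS given RVC. In the illustration that gives 0.91 SD with sensitivity 0.67 and specificity 0.87. The contrast with 1.81 SD and 0.22 requires the less natural reading, bivariate normality, 10% prevalence at the visit analysed, and a table evaluated at the item 4 cut-off, which the plan does not specify.

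The result is secondary and descriptive. BIS results are blinded and only RVC counts as indicative of lymphedema during the study (Section 5.3). The tau estimates, their intervals and the target of 200 patients are unaffected. The choice of estimator is a fair trade-off, and an analyst who states the method beside the estimate gives readers what they need.
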